5.2.2. Dosage and Administration

Detailed information regarding the preparation and administration of EFX or placebo for this study is contained in the EFX Pharmacy Manual. Investigational medicinal product will be administered by subcutaneous injection once weekly as follows:

- Placebo QW (n = 40)
- 28 mg EFX QW (n = 40)
- 50 mg EFX QW (n = 40)

The IMP will be administered by a weekly 1.0 mL subcutaneous injection into the abdomen by a qualified staff member at the clinic or utilizing in-home nursing. The date and time of injection will be recorded. If injection site reactions are observed, mitigation procedures should be put in place as per local standard of care. Examples of mitigations include icing

the injection site, rotating the quadrant of the abdomen in which the injection is administered, or providing antihistamine prior to injection.

If subjects are unable to attend study visits and/or study centers are unable to accommodate on-site visits due to pandemics, natural disasters, or other major disruptions procedures will be put in place to allow for direct-to-subject drug shipments for utilization of in-home nursing, as necessary.

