6.25.1. Hepatic Events Adjudication Committee

A key objective of this study is to prevent progression to cirrhosis and associated complications. Clinical events that constitute the clinical outcomes endpoint include:

- 1) Progression to cirrhosis as defined by a liver biopsy showing F4 fibrosis according to the NASH CRN classification, as assessed by the central reader.
- 2) Events of hepatic decompensation including:

- a) Clinically apparent ascites requiring treatment
- b) HE of Grade 2 or above (according to the West Haven criteria defined in [Appendix E](#)) requiring treatment
- c) Portal hypertension-related upper gastrointestinal bleeding identified by endoscopy and requiring hospitalization, including events of bleeding from esophageal varices, gastric varices, and portal hypertensive gastropathy
- 3) Liver transplantation or qualification for liver transplantation, defined as MELD score ≥ 15 (unless due to therapeutic anticoagulation) on at least 2 consecutive occasions at least 4 weeks apart
- 4) All-cause mortality

Each of the clinical events (except histologic progression to cirrhosis, all-cause mortality and liver transplantation) will require confirmation by a Hepatic Events Adjudication Committee. All deaths will be reviewed by this committee to determine if they are liver-related.

If there is clinical evidence that a subject has progressed to cirrhosis (e.g., based on the presence of new esophageal varices, changes in biomarkers [including, but not limited to, low serum albumin, high serum bilirubin, a low platelet count, prolonged INR, or elevated liver stiffness], or development of other clinical signs or symptoms of cirrhosis), the subject should undergo repeat liver biopsy for confirmation of progression to cirrhosis (F4 fibrosis as assessed by the central reader according to the NASH CRN classification) at the discretion of the principal investigator (PI).

Once the clinical event (except histological progression to cirrhosis, all-cause mortality and liver transplantation) is confirmed by the Hepatic Events Adjudication Committee, the subject will discontinue from the study. Subjects who experience histological progression to cirrhosis, all-cause mortality and liver transplantation will be discontinued from the study, but do not require confirmation from the adjudication committee prior to discontinuation.

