10. APPENDICES

Appendix A. Schedule of Assessments – Screening to Week 24

Assessments ^a	Screening ^t (- 8 wks)	Pre-Baseline ^b (-4 wks)	Baseline / Day 1	Week 1	Weeks 2 & 3	Week 4	Week 8	Week 12	Week 16	Week 20	Weeks 5, 6, 7, 9, 10, 11, 13, 14, 15, 17, 18, 19, 21, 22, 23 ^c	Week 24	Early Term & 30-Day Follow-Up ^r
Clinical Assessments													
Written Informed Consent	X												
Eligibility	X	X	X										
Medical History	X												
Physical Examination ^d	X		X	X		X	X	X	X	X		X	X
Child-Pugh Score ^d			X					X				X	X
Vital Signs ^e	X	X	X	X	X	X	X	X	X	X		X	X
Weight ^f	X	X	X	X	X	X	X	X	X	X		X	X
Height	X												
Hip and Waist Circumference ^f	X		X					X				X	X
12-lead ECG	X		X									X	X
FibroScan® ^g	X											X	X
MRI-PDFF	X											X	X ^s
DXA	X												
Liver Biopsy ^a	X											X	X ^s
CLDQ-NASH ^h			X					X				X	

Assessments ^a	Screening ^t (- 8 wks)	Pre-Baseline ^b (-4 wks)	Baseline / Day 1	Week 1	Weeks 2 & 3	Week 4	Week 8	Week 12	Week 16	Week 20	Weeks 5, 6, 7, 9, 10, 11, 13, 14, 15, 17, 18, 19, 21, 22, 23 ^c	Week 24	Early Term & 30-Day Follow-Up ^t
Clinical Assessments													
Lifestyle Guidance ⁱ	X		X	X	X	X	X	X	X	X		X	
Administer Study Drug ^j			X	X	X	X	X	X	X	X	X	X	
Concomitant Medications	X	X	X	X	X	X	X	X	X	X	X	X	X
Adverse Events	X ^k	X	X	X	X	X	X	X	X	X	X	X	X
Laboratory Assessments													
Chemistry, Hematology, Lipids, Coagulation ^l	X	X ^m	X	X		X	X	X	X	X		X	X
Serum & Plasma Storage Samples ⁿ			X	X		X	X	X	X	X		X	X
Urine drug screen	X												
Serologies ^l	X												
Fibrosis Biomarkers ^l			X					X				X	X
Other Biomarkers ^l			X			X		X				X	X
PK ^o			X			X	X		X			X	X
ADA and NAB ^p			X				X		X			X	X
Endogenous FGF21			X				X		X			X	X
							■						
Pregnancy testing ^q	X		X			X	X	X	X	X		X	X

ADA = anti-drug antibodies; BP = blood pressure; ECG = electrocardiogram; HR = heart rate; PE = Physical Examination; PK = pharmacokinetic; NAB = neutralizing antibody

a All visits after Baseline (Day 1) can be performed within the following window: \pm 3 days for weekly visits 1 - 24. Liver Biopsies should be obtained within (-) 2 weeks to (+) 4 weeks of the scheduled Week 24 visit date. MRI-PDFF to be obtained \pm 5 days from the liver biopsy.

b If no historical ALT/AST measurements available, visit is required to confirm no worsening of ALT/AST.

- c Subjects will have the option to conduct visit using in-home nursing.

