Appendix B. Schedule of Assessments – Long-Term Follow-Up

Assessments ^a	Weeks 28, 36, 44, 52	Week 32, 40	48	Weeks 56, 64, 80, 88	Week 72	Weeks 96	Early Term & 30-Day Follow-Up ¹
Clinical Assessments							
Physical Examination	X	X	X ^b	X	X	X	X
Child Pugh Score ^b			X			X	X
Vital Signs ^c	X	X	X	X	X	X	X
Weight ^d	X	X	X	X	X	X	X
Hip and Waist Circumference ^d	X	X	X	X	X	X	X
12-lead ECG			X			X	X
FibroScan ^{®e}			X			X	
MRI-PDFF						X ^m	X ^o
DXA			X ^p			X	
Liver Biopsy						X ^m	X ^o
CLDQ-NASH ^f	X		X			X	
Lifestyle Guidance ^g	X	X	X	X	X	X	
Administer Study Drug ^h	X	X	X	X	X	X	
Concomitant Medications	X	X	X	X	X	X	X
Adverse Events	X	X	X	X	X	X	X
Laboratory Assessments							
Chemistry, Hematology, Lipids, Coagulation ⁱ	X	X	X	X	X	X	X
Serum & Plasma Storage Samples ^j	X	X	X	X	X	X	X

[figure not shown]
Assessments ^a	Weeks 28, 36, 44, 52	Week 32, 40	48	Weeks 56, 64, 80, 88	Week 72	Weeks 96	Early Term & 30-Day Follow-Up ¹
Fibrosis Biomarkers ⁱ			X		X	X	X
Other Biomarkers ⁱ		X	X		X	X	X
PK		X	X	X	X	X	X
ADA and NAB ⁿ		X	X	X	X	X	X
Endogenous FGF21		X	X	X	X	X	X
Pregnancy testing ^k	X	X	X	X	X	X	X

ADA = anti-drug antibodies; BP = blood pressure; ECG = electrocardiogram; HR = heart rate; PE = Physical Examination; PK = pharmacokinetic; NAB = neutralizing antibody

- a In-clinic visits will be conducted every 4 weeks \pm 5 days from Week 28 to Week 56 and then every 8 weeks \pm 7 days from Week 64 to Week 96.
- b Complete PE including assessment at Week 48, otherwise symptom-driven. Child-Pugh (CP) Score assessments should be completed as part of the physical exam at Week 48, Week 96, and ET & 30-Day Follow-up.
- c Vitals to include systolic and diastolic BP, pulse, respiration rate will be collected at each visit. Triplicate blood pressure (to be measured in same arm with at least two minutes rest between BP measurements) and heart rate to be collected at Week 48 and Week 96. Single measurements to be collected at all other visits.
- d Weight, waist and hip circumference should be obtained by the same study personnel as much as possible across visits for each subject to minimize variability in the measurement. On dosing days, weight will be collected pre-dose. Weight should be obtained using a calibrated scale. The subject should be weighed in consistent clothing.
- e At least 2-3 hours fasting is required prior to all elastography assessments.

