7.1 General Principles

All data processing, summarization and analyses will be performed using Fortrea's SAS Environment / Version 9.4 (or later) of the SAS® statistical software package.

The following principles will be applied to all tables, figures, and listings (TFLs) unless otherwise stated:

Principle	Value
Significant tests	Two-sided and use a 5% significance level for main effects and 10% significance level for interaction terms.
Treatment group labels and order presented	Placebo EFX 28 mg EFX 50 mg All EFX (as applicable) Total (as applicable)
Tables	Data in summary tables presented by assessment or parameter, treatment group, and visit (where applicable).
Listings	All individual subject data will be listed as measured and presented by treatment group, subject, and visit (where applicable), unless otherwise specified.
Descriptive summary statistics for continuous variables	Number of non-missing values (n), arithmetic mean, arithmetic standard deviation (SD), median and range (minimum and maximum). Descriptive statistics for certain continuous data will include geometric mean and geometric coefficient of variation. PK concentrations will be summarized with the set of continuous parameters including geometric mean and will add the statistic of number of samples below the limit of quantification (BLQ).
Descriptive summary statistics for categorical variables	Frequency counts and percentages [n (%)].
Denominator for percentages	Number of subjects in the analysis set, unless stated otherwise in table shell.
Include "Missing" as category	Demographics and Other Baseline Characteristics only.

Statistical Analysis Plan

Sponsor Name: Akero Therapeutics, Inc.
Sponsor Protocol ID: AK-US-001-0102

Principle	Value
Display for 0 percentages	Blank
Display collected value	Minimum and maximum
Display 1 decimal place	Q1 (25 th Percentile), Q3 (25 th Percentile), Mean, Mean Difference, Median, Standard Deviation, and Confidence Interval for all parameters except DXA parameters.
Display 3 decimal places	Q1 (25 th Percentile), Q3 (25 th Percentile), Mean, Mean Difference, Median, Standard Deviation, and Confidence Interval for DXA parameters; p-value.
Limit of precision for displays	1 decimal place, unless otherwise specified.
Date Format	DDMMYYYY

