7.1.1 Definition of Baseline

For all variables except lipids, liver enzymes variables, and blood pressure, pre-dose measurements on Baseline visit (Day 1) will be considered the baseline values. If the measurement at this visit is not available, the last available measurement (including unscheduled visit) prior to the first dose of study drug may be used as the baseline value unless it is stated otherwise. The scheduled baseline visit for FibroScan, liver biopsy, MRI-PDFF, and DXA scan is Screening.

Baseline lipid variables including Total Cholesterol, HDL-C, LDL-C, Triglycerides, non-HDL-C, VLDL-C, VLDL-T, HDL-P, IDL-P, LDL-P, VLDL-T-P, HDL particle size, LDL particle size, VLDL particle size, Lp (a), and lipoprotein insulin resistance will be the average of Screening and Baseline visit (Day 1) values. If one is missing, the available one will be used.

Baseline liver enzymes variables including ALT, AST and ALP will be the average of Pre-Baseline and Baseline visit (Day 1) values. If one is missing, the available one will be used. If both are missing, the available Screening value will be used.

Baseline blood pressure will be the average of Screening, Pre-Baseline, and Baseline visit (Day 1) values. If one value is missing, the average of the two available values will be used. If two values are missing, the available one will be used.

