7.6.3.7 Changes in cardiovascular and metabolic risk factors

The analysis of changes in cardiovascular and metabolic risk factors will be performed using the Safety Set. Descriptive summaries and boxplots of BMI and blood pressure will be presented by treatment group and visit.

An MMRM model with baseline covariate will be used to evaluate the changes from baseline in blood pressure between the EFX arms and the placebo arm at scheduled visits, controlling for stratification factors. Least square (LS) means, 95% CIs, and p-values will be presented. The analysis will be performed using the Safety Set.

A CMH test will be used to compare the differences in proportions of subjects with new onset of T2D between the EFX arms and the placebo arm, adjusting for stratification factors. The new onset of T2D is defined as a single HbA1C value of 6.5% or higher when baseline HbA1c <6.5%. The analysis will be performed using the Safety Set.

7.6.3.8 Non-invasive measures of fibrosis can predict histological regression and/or progression of fibrosis and clinical complications of cirrhosis

Correlation models will be fitted to explore the correlation coefficient between non-invasive measures of fibrosis and histological fibrosis (CRN fibrosis stage of liver biopsy) and clinical complications of cirrhosis (MELD score and CP score). Non-invasive measures of fibrosis include serum biomarkers (ELF and Pro-C3) and imaging (liver stiffness by FibroScan). In addition, correlation between the imaging marker for hepatic fat (MRI-PDFF) and histological fibrosis and NASH resolution will also be explored. The analysis will be performed using the LBAS.

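### New-onset T2D rests on one unconfirmed HbA1c at or above the same 6.5% cut-off that defines the at-risk baseline, so measurement noise alone can create cases

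*SAP*

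**What the plan says.** SAP 7.6.3.7 gives the rule: "The new onset of T2D is defined as a single HbA1C value of 6.5% or higher when baseline HbA1c <6.5" (percent). It also gives the use: "A CMH test will be used to compare the differences in proportions of subjects with new onset of T2D between the EFX arms" and placebo, stratified, on the Safety Set. SAP 7.1 makes tests "Two-sided and use a 5% significance level for main effects".

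HbA1c is not among the variables with an averaged baseline in SAP 7.1.1 (lipids, liver enzymes, blood pressure). It falls under the general rule that "pre-dose measurements on Baseline visit (Day 1) will be considered the baseline values", so one Day 1 reading decides who is at risk. SAP 6.2 plans no outlier rule.

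The number of readings depends on which document is followed. Protocol Table 5 lists HbA1c in the chemistry column, and Appendices A and B schedule "Chemistry, Hematology, Lipids, Coagulation" at every main visit. The SAP's own chemistry list (SAP Table 5) leaves HbA1c out. SAP 3.2 and 7.6.2.6 treat it as a glycemic marker, a group with fewer windows in SAP 6.1.

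Elsewhere the trial does confirm a threshold event. Protocol 6.25.1 counts MELD of 15 or more only "on at least 2 consecutive occasions at least 4 weeks apart".

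**The concern.** The value that ends at-risk status is the value that defines it, and the first crossing counts. A stable subject a little below 6.5% gets a fresh chance of crossing at each sample, so the number of cases rises with the number of samples even if nobody's glycemia changes. An arm followed longer, or sampled more completely, collects more of them.

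At stake is the reading of one exploratory comparison. The reported incidence would mix true new diabetes with noise, and the arm difference could be distorted in either direction. The protocol's phase 2a summary (1.4.1.3) reports HbA1c reductions of 0.39 points at 50 mg and 0.50 at 70 mg. A downward shift of that kind moves subjects away from the cut-off and reduces noise-made cases on EFX only.

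**Working it through.** **No stated figure to reproduce.** The documents give no expected incidence or power for new-onset T2D.

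**Number of readings.**
- Protocol Appendix A, chemistry: Weeks 1, 4, 8, 12, 16, 20, 24 = 7.
- Protocol Appendix B, in-clinic visits every 4 weeks "from Week 28 to Week 56 and then every 8 weeks": Weeks 28, 32, 36, 40, 44, 48, 52, 56 (8), then 64, 72, 80, 88, 96 (5) = 13.
- Total 7 + 13 = 20, equal to the 20 chemistry windows in SAP 6.1.
- SAP 6.1 glycemic-marker windows: Weeks 4, 12, 24, 32, 40, 48, 72, 96 = 8. SAP 6.1 assigns scheduled visits as recorded on the eCRF, so these windows do not by themselves remove the other scheduled HbA1c values.

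**One stable subject.** Let μ be the true value, constant and below 6.5, and σ the within-subject SD. σ is not in the documents; 0.15 is assumed here. Readings are taken as independent given μ.
- One reading: p = 1 − Φ((6.5 − μ)/σ).
- At least one of K: 1 − (1 − p)^K.
- Two consecutive among K: a₁ = 1 − p, b₁ = p; a(k+1) = (a(k) + b(k))(1 − p), b(k+1) = a(k)·p; probability = 1 − a(K) − b(K).

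| True HbA1c | One reading | Any of 8 | Any of 20 | Two consecutive, 8 | Two consecutive, 20 |
|---|---|---|---|---|---|
| 6.1% | 0.4% | 3.0% | 7.4% | 0.0% | 0.0% |
| 6.2% | 2.3% | 16.8% | 36.9% | 0.4% | 1.0% |
| 6.3% | 9.1% | 53.5% | 85.2% | 5.3% | 13.7% |
| 6.4% | 25.2% | 90.3% | 99.7% | 32.4% | 64.9% |

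Example at 6.2%: p = 1 − Φ(0.3/0.15) = 1 − Φ(2) = 0.0228; 1 − 0.9772^20 = 0.369. If results are reported to 0.1%, a reading of 6.45 counts as 6.5, and this row becomes 32% (8) and about 62% (20). With σ = 0.10 and no rounding it is 1.1% and 2.7%.

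**At-risk population.** Simulation of 400,000 subjects per setting, with true values normal (mean 5.8%, an assumption) and cut off below 6.5, observed baseline below 6.5, σ = 0.15 and no true change.

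| Between-subject SD | Rounded to 0.1 | Single value: 8 / 20 visits | Two consecutive: 8 / 20 visits |
|---|---|---|---|
| 0.30 | no | 4.3% / 7.0% | 0.8% / 1.7% |
| 0.30 | yes | 6.0% / 9.3% | 1.3% / 2.5% |
| 0.35 | no | 5.8% / 8.7% | 1.3% / 2.4% |
| 0.35 | yes | 7.4% / 11.1% | 1.9% / 3.4% |

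Varying the mean over 5.7-5.9% and σ over 0.10-0.20 (rounded, 20 visits) gives about 2% to 25%. With visit-to-visit autocorrelation of 0.4, the last row's 20-visit rates become about 10% (single) and 4.7% (two consecutive).

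**Denominator.** These are rates among subjects with baseline below 6.5%. SAP 7.1 uses the whole analysis set by default, and subjects with T2D are enrolled. If half of a 40-subject arm (Protocol 5.2.2) were at risk, 7-11% of 20 is 1.4 to 2.2 subjects, or 3.5-5.5% of the arm.

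**Effect on the comparison.**
- Dilution, equal noise in both arms: assume true incidence 15% vs 5%, with 10% of non-cases made false cases. Then 0.15 + 0.85 × 0.10 = 0.235 and 0.05 + 0.95 × 0.10 = 0.145. The risk ratio falls from 3.0 to 1.62, and power at 40 per arm from 32% to 17%.
- Separation, EFX lowers HbA1c: in the last simulation row (20 visits), a fall of 0.1, 0.2 or 0.3 points takes the EFX false rate from 11.1% to about 5.6%, 2.2% or 0.6%, while placebo stays at 11.1%. At 0.3 the spurious gap is 11.1 − 0.6 = 10.5 points, with nobody truly reaching 6.5%. With two consecutive values it is about 3.4.

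**The case against.** The sizes rest entirely on assumed inputs. This stands: the tables support the mechanism and an order of magnitude, not a prediction. Eight readings may well be the intended count, given how the SAP classes HbA1c. That also stands, and the point holds at 8.

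Three stronger readings are tempting and are not supported:
- A reader might infer that noise swamps true new diabetes. The documents give no true incidence, so that comparison cannot be made.
- A reader might infer that the test is always pulled toward no difference. That requires equal noise in all arms. The phase 2a HbA1c falls make the opposite distortion equally plausible, although the protocol does not report them separately for subjects without diabetes.
- A reader might infer that the rule selects subjects just below the cut-off. It admits any baseline below 6.5%; noise matters mainly for those near it.

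The MELD precedent is also mixed. Protocol 6.25.1 requires two values, but Protocol Table 6 treats the same MELD threshold as non-response without stating any confirmation. It shows that confirmation is workable here, not that it is the trial's general standard.

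Finally, change in HbA1c is a secondary endpoint with its own MMRM (SAP 7.6.2.6), so glycemic conclusions do not depend on this count.

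**Conclusion.** The concern holds in limited form. The rule as written lets noise create cases among subjects who stay below 6.5%, and nothing elsewhere in the documents adds confirmation. Under the assumptions shown, false cases are about 4-7% of at-risk subjects over 8 visits and 7-11% over 20; the proportion in the Safety Set is lower. They inflate the count, grow with sampling, and can either dilute a true difference or make a mean HbA1c shift look like prevention. Which of these occurs cannot be settled from the documents. The analysis is exploratory, so this is a worthwhile, low-cost improvement rather than a threat to any primary or secondary result. Whether subjects with known T2D should be counted at all is a separate question.

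**What to change.** In SAP 7.6.3.7, for analysis purposes only:
- Define new-onset T2D as HbA1c of 6.5% or higher at two consecutive scheduled post-baseline HbA1c visits, dated at the first.
- Define consecutive by nominal visit, not by a minimum of 28 calendar days. With visit windows of ±3 or ±5 days, and visits falling uniformly within them, about 43-45% of adjacent 4-weekly pairs would be less than 28 days apart.
- Name the visit set that applies (the 8 glycemic-marker visits or the 20 chemistry visits), and reconcile SAP 6.1 with Protocol Table 5.
- Report separately, as unconfirmed, a single value at or above 6.5% at the last available sample, or one followed by a start or increase of antidiabetic medication before the next sample.
- Keep the single-value count as a supporting summary. An unblinded sponsor team reviews the Week 24 results (SAP 7.9), so showing both counts also makes clear that the definition was not chosen for its result.

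Cost: a short SAP paragraph and no new samples. Fewer cases will be counted and some true ones left unconfirmed, especially on the 8-visit schedule, where the last samples are 24 weeks apart. Confirmation reduces false cases but does not remove them within about 0.1 of the cut-off: at a true 6.4% and σ = 0.15, 32% (8 visits) to 65% (20 visits) would still qualify.
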